6.0 Renal Toxicities	
	If elevations persist 3-5 days or worsen, consider additional immunosuppression (e.g, mycophenolate)
G4	If improved to G1, taper corticosteroids over at least 4 weeks If elevations persist 2-3 days or worsen, consider additional immunosuppression (e.g, mycophenolate)
All recommendations are expert consensus based, with benefits outweighing harms, and strength of recommendations are moderate.	

Abbreviations: AKI, acute kidney injury; G, Grade; ICPI, immune checkpoint inhibitor; irAE, immune-related adverse event; IV, intravenous; ULN, upper limit of normal; UTI, urinary tract infection.

Table A7

Management of Nervous System irAEs in Patients Treated With ICPis

7.0 Nervous System Toxicities	
7.1 Myasthenia gravis	
Definition: Fatigable or fluctuating muscle weakness, generally more proximal than distal. Frequently has ocular and/or bulbar involvement (ptosis, extraocular movement abnormalities resulting in double vision, dysphagia, dysarthria, facial muscle weakness). May have neck and/or respiratory muscle weakness. (Note: May occur with myositis and/or myocarditis). Respiratory symptoms may require evaluation to rule out pneumonitis, myocarditis. Miller Fisher variant of Guillain-Barré syndrome (ophthalmoparesis) and the oculobulbar myositis (ptosis, ophthalmoparesis, dysphagia, neck and respiratory weakness) with ICPi may have overlapping symptoms.	
Grading	Management
All grades	All grades warrant work-up and intervention given potential for progressive myasthenia gravis to lead to respiratory compromise
No G1	
G2: Some symptoms interfering with ADL MGFA severity class 1 (ocular symptoms and findings only) and MGFA severity class 2 (mild generalized weakness)	Hold ICPi and may resume in G2 patients (MGFA 1 and 2) only if symptoms resolve Should consult neurology Pyridostigmine starting at 30 mg orally three times a day and gradually increase to maximum of 120 mg orally four times a day as tolerated and based on symptoms Administer corticosteroids (prednisone, 1-1.5 mg/kg orally daily) if symptoms G2; wean based on symptom improvement
G3-4: Limiting self-care and aids warranted, weakness limiting walking, ANY dysphagia, facial weakness, respiratory muscle weakness, or rapidly progressive symptoms, or MGFA severity class 3-4 moderate to severe generalized weakness to myasthenic crisis	Permanently discontinue ICPi Admit patient, may need ICU-level monitoring Neurology consult Continue corticosteroids and initiate IVIG 2 g/kg IV over 5 days (0.4 g/kg/d) or plasmapheresis for 5 days Frequent pulmonary function assessment Daily neurologic review
Additional considerations	Avoid medications that can worsen myasthenia: β -blockers, IV magnesium, fluoroquinolones, aminoglycosides, and macrolides Initially a 5-day course of plasmapheresis or a 2 g/kg course of IVIG over 5 days 1-2 mg/kg methylprednisolone daily, wean based on symptom improvement Pyridostigmine, wean based on improvement ICPi-associated myasthenia gravis may be monophasic, and additional corticosteroid-sparing agents may not be required

7.0 Nervous System Toxicities**7.2 Guillain-Barré syndrome**

Definition: Progressive, most often symmetrical muscle weakness with absent or reduced deep tendon reflexes. Often starts with sensory symptoms/neuropathic pain localized to lower back and thighs. May involve extremities (typically ascending weakness but not always), facial, respiratory, and bulbar and oculomotor nerves. May have dysregulation of autonomic nerves.

Diagnostic work-up

Neurologic consultation

MRI of spine with or without contrast (rule out compressive lesion and evaluate for nerve root enhancement/thickening)

Lumbar puncture: CSF typically has elevated protein and often elevated WBCs; even though this is not typically seen in classic Guillain-Barré syndrome, cytology should be sent with any CSF sample from a patient with cancer.

Serum antibody tests for Guillain-Barré syndrome variants (GQ1b for Miller Fisher variant a/w ataxia and ophthalmoplegia) Electrodiagnostic studies to evaluate polyneuropathy

Pulmonary function testing (NIF/VC)

Frequent neurochecks

Grading	Management
All grades	Warrant work-up and intervention given potential for progressive Guillain-Barré syndrome to lead to respiratory compromise Note: There is no G1 toxicity
G1: Mild, none	NA
G2: Moderate, some interference with ADL, symptoms concerning to patient	Discontinue ICPi
G3-4: Severe, limiting self-care and aids warranted, weakness, limiting walking, ANY dysphagia, facial weakness, respiratory muscle weakness, or rapidly progressive symptoms	Permanently discontinue ICPi. Admission to inpatient unit with capability of rapid transfer to ICU-level monitoring Start IVIG (0.4 g/kg/d for 5 days for a total dose of 2 g/kg) or plasmapheresis. Corticosteroids are usually not recommended for idiopathic Guillain-Barré syndrome; however, in ICPi-related forms, a trial is reasonable (methylprednisolone 2-4 mg/kg/d), followed by slow corticosteroid taper Pulse corticosteroid dosing (methylprednisolone 1 g/d for 5 days) may also be considered for G3-4 along with IVIG or plasmapheresis Frequent neurochecks and pulmonary function monitoring Monitor for concurrent autonomic dysfunction Nonopioid management of neuropathic pain Treatment of constipation/ileus

Additional considerations

Slow prednisone taper after corticosteroid pulse plus IVIG or plasmapheresis May require repeat IVIG courses

Caution with rechallenging for severe cases

7.3 Peripheral neuropathy

Definition: Can present as asymmetric or symmetric sensory, motor, or sensory motor deficit. Focal mononeuropathies, including cranial neuropathies (e.g. facial neuropathies/Bell palsy) may be present. Numbness and paresthesias may be painful or painless. Hypo- or areflexia or sensory ataxia may be present.

Diagnostic work-up

G1

Screen for reversible neuropathy causes: diabetic screen, B12, folate, TSH, HIV, consider serum protein electrophoresis, and other vasculitic and autoimmune screen Neurologic consultation

7.0 Nervous System Toxicities	
Consider MRI of spine with or without contrast G2: in addition to above MRI spine advised/MRI of brain if cranial nerve Consider EMG/NCS Consider neurology consultation G3-4: go to Guillain-Barré syndrome algorithm	
Grading	Management
G1: Mild, no interference with function and symptoms not concerning to patient. Note: Any cranial nerve problem should be managed as moderate	Low threshold to hold ICPi and monitor symptoms for a week If to continue, monitor very closely for any symptom progression
G2: Moderate, some interference with ADL, symptoms concerning to patient (i.e, pain but no weakness or gait limitation)	Hold ICPi and resume once return to G1 Initial observation OR initiate prednisone 0.5-1 mg/kg (if progressing from mild) Neurontin, pregabalin, or duloxetine for pain
G3-4: Severe, limiting self-care and aids warranted, weakness limiting walking or respiratory problems (i.e, leg weakness, foot drop, rapidly ascending sensory changes) Severe may be Guillain-Barré syndrome and should be managed as such	Permanently discontinue ICPi Admit patient Neurologic consultation Initiate IV methylprednisolone 2-4 mg/kg and proceed as per Guillain-Barré syndrome management
7.4 Autonomic neuropathy	
Definition: Nerves that control involuntary bodily functions are damaged. This may affect blood pressure, temperature control, digestion, bladder function, and sexual function. A case of severe enteric neuropathy with ICPi has been reported. Can present with GI difficulties such as new severe constipation, nausea, urinary problems, sexual difficulties, sweating abnormalities, sluggish pupil reaction, and orthostatic hypertension.	
Diagnostic work-up An evaluation by neurologist or relevant specialist, depending on organ system, with testing that may include Screening for other causes of autonomic dysfunction: diabetic screen, adrenal insufficiency, HIV, paraproteinemia, amyloidosis, botulism; consider chronic diseases such as Parkinson and other autoimmune screening AM orthostatic vitals Consider electrodiagnostic studies to evaluate for concurrent polyneuropathy Consider paraneoplastic Lambert-Eaton myasthenic syndrome, antineutrophil cytoplasmic antibodies, and ganglionic AChR antibody testing	
Grading	Management
G1: Mild, no interference with function and symptoms not concerning to patient	Low threshold to hold ICPi and monitor symptoms for a week; if to continue, monitor very closely for any symptom progression
G2: Moderate, some interference with ADL, symptoms concerning to patient	Hold ICPi and resume once return to G1 Initial observation OR initiate prednisone 0.5-1 mg/kg (if progressing from mild) Neurologic consultation
G3-4: Severe, limiting self-care and aids warranted	Permanently discontinue ICPi Admit patient Initiate methylprednisolone 1 g daily for 3 days followed by oral corticosteroid taper Neurologic consultation
7.5 Aseptic meningitis	
Definition: may present with headache, photophobia, and neck stiffness; often afebrile but may be febrile. There may be nausea/vomiting. Mental status should be normal (distinguishes from encephalitis). Diagnostic work-up MRI of brain with or without contrast + pituitary protocol AM cortisol, ACTH to rule out adrenal insufficiency	

7.0 Nervous System Toxicities	

Consider lumbar puncture: measure opening pressure; check cell count and protein glucose; and perform Gram stain, culture, PCR for HSV, and other viral PCRs depending on suspicion, cytology
 
May see elevated WBC count with normal glucose, normal culture, and Gram stain; may see reactive lymphocytes or histiocytes on cytology
	
Grading	Management

G1: Mild, no interference with function and symptoms not concerning to patient. Note: Any cranial nerve problem should be managed as moderate.
 
G2: Moderate, some interference with ADL, symptoms concerning to patient (i.e. pain but no weakness or gait limitation)
 
G3-4: Severe, limiting self-care and aids warranted
	
Hold ICPi and discuss resumption with patient only after taking into account the risks and benefits, consider empirical antiviral (IV acyclovir) and antibacterial therapy until CSF results Once bacterial and viral infection are negative, may closely monitor off corticosteroids or consider oral prednisone 0.5-1 mg/kg or IV methylprednisolone 1 mg/kg if moderate/severe symptoms

7.6 Encephalitis	

Definition: As for aseptic meningitis, need to exclude infectious causes, especially viral (i.e. HSV).
 
Confusion, altered behavior, headaches, seizures, short-term memory loss, depressed level of consciousness, focal weakness, speech abnormality
	

Diagnostic work-up
 
Neurologic consultation
 
MRI of brain with or without contrast may reveal T2/fluid-attenuated inversion recovery changes typical of what is seen in autoimmune encephalopathies or limbic encephalitis or may be normal
 
Lumbar puncture: check cell count and protein glucose and perform Gram stain, culture, PCR for HSV and other viral PCRs depending on suspicion, cytology, oligoclonal bands, autoimmune encephalopathy, and paraneoplastic panels.
 
May see elevated WBC count with lymphocytic predominance and/or elevated protein
 
EEG to evaluate for subclinical seizures
 
Blood: metabolic, CBC, ESR, CRP, ANCA (if suspect vasculitic process), thyroid panel including TPO and thyroglobulin Rule out concurrent anemia/thrombocytopenia, which can present with severe headaches and confusion
	
Grading	Management

G1: Mild, no interference with function and symptoms not concerning to patient. Note: Any cranial nerve problem should be managed as moderate.
 
G2: Moderate, some interference with ADL, symptoms concerning to patient (i.e. pain but no weakness or gait limitation)
 
G3-4: Severe, limiting self-care and aids warranted
	
Hold ICPi and discuss resumption with patient only after taking into account the risks and benefits
 
As above for aseptic meningitis suggest concurrent IV acyclovir until PCR results obtained and negative
 
Trial of methylprednisolone 1-2 mg/kg
 
If severe or progressing symptoms or oligoclonal bands present, consider pulse corticosteroids methylprednisolone 1 g IV daily for 3-5 days plus IVIG 2 g/kg over 5 days If positive for autoimmune encephalopathy antibody and limited or no improvement, consider rituximab or plasmapheresis in consultation with neurology.

7.7 Transverse myelitis	

Definition: Acute or subacute weakness or sensory changes bilateral, often with increased deep tendon reflexes
	

Diagnostic work-up
 
Neurologic consultation
 
MRI of spine (with thin axial cuts through the region of suspected abnormality) and MRI of brain
 
Lumbar puncture: cell count, protein, glucose, oligoclonal bands, viral PCRs, cytology, onconeural antibodies
 
Blood: B12, HIV, RPR, ANA, Ro/La, TSH, aquaporin-4 IgG
 
Evaluation for urinary retention, constipation
	

7.0 Nervous System Toxicities	
Grading	Management
G1: Mild, no interference with function and symptoms not concerning to patient. Note: Any cranial nerve problem should be managed as moderate.	Permanently discontinue ICPi Methylprednisolone 2 mg/kg
G2: Moderate, some interference with ADL, symptoms concerning to patient (i.e, pain but no weakness or gait limitation)	Strongly consider higher doses of 1 g/d for 3-5 days Strongly consider IVIG
G3-4: Severe, limiting self-care and aids warranted	
All recommendations are expert consensus based, with benefits outweighing harms, and strength of recommendations are moderate.	

Abbreviations: AChR, acetylcholine receptor; ACTH, adrenocorticotropic hormone; ADL, activities of daily living; ANA, antinuclear antibody; ANCA, antineutrophil cytoplasmic antibodies; CBC, complete blood count; CNS, central nervous system; CPK, creatine phosphokinase; CRP, C-reactive protein; CSF, cerebrospinal fluid; ECG, electrocardiogram; EEG, electroencephalogram; EMG, electromyography; ESR, erythrocyte sedimentation rate; G, Grade; GI, gastrointestinal; HIV, human immunodeficiency virus; HSV, herpes simplex virus; ICPi, immune checkpoint inhibitor; ICU, intensive care unit; IgG, immunoglobulin G; irAE, immune-related adverse event; IV, intravenous; IVIG, intravenous immunoglobulin; MGFA, Myasthenia Gravis Foundation of America; MRI, magnetic resonance imaging; NA, not applicable; NCS, nerve conduction study; NIF, negative inspiratory force; PCR, polymerase chain reaction; RPR, rapid plasma reagin; TPO, thyroid peroxidase; TSH, thyroid-stimulating hormone; TTE, transthoracic echocardiogram; VC, vital capacity; WBC, white blood cell.

Table A8

Management of Hematologic irAEs in Patients Treated With ICPis

8.0 Hematologic Toxicities	
8.1 Autoimmune hemolytic anemia	
Definition: A condition in which RBCs are destroyed and removed from the blood stream before their normal lifespan is over. Symptoms include weakness, paleness, jaundice, dark-colored urine, fever, inability to do physical activity, and heart murmur.	
Diagnostic work-up	
History and physical examination (with special consideration of history of new drugs and insect, spider, or snake bites)	
Blood chemistry, CBC with evidence of anemia, macrocytosis, evidence of hemolysis on peripheral smear; LDH, haptoglobin, bilirubin, reticulocyte count, free Hgb DIC panel, which could include PTNIR infectious causes	
Autoimmune serology	
Paroxysmal nocturnal hemoglobinuria screening	
Direct and indirect bilirubin; LDH; direct agglutinin test; and if no obvious cause, bone marrow analysis, cytogenetic analysis to evaluate for myelodysplastic syndromes	
Evaluation for viral/bacterial (mycoplasma, etc) causes of hemolysis studies	
Protein electrophoresis, cryoglobulin analysis	
Work-up for bone marrow failure syndrome if refractory, including B12, folate, copper, parvovirus, FE, thyroid, infection	
Glucose-6-phosphate dehydrogenase	
Evaluation of common drug causes (ribavirin, rifampin, dapsone, interferon, cephalosporins, penicillins, NSAIDs, quinine/quinidine, fludarabine, ciprofloxacin, lorazepam, diclofenac, etc)	
Assessment of methemoglobinemia	
Grading	Management
G1: Hgb < LLN to 10.0 g/dL; < LLN to 6.2 mmol/L; < LLN to 100 g/L	Continue ICPi with close clinical follow-up and laboratory evaluation
G2: Hgb < 10.0 to 8.0 g/dL; < 6.2 to 4.9mmol/L; < 100 to 80 g/L	Hold ICPi and strongly consider permanent discontinuation Administer 0.5-1 mg/kg/d prednisone equivalents
G3: Hgb < 8.0 g/dL; < 4.9 mmol/L; < 80 g/L; transfusion indicated	Permanently discontinue ICPi Should use clinical judgment and consider admitting the patient Hematology consult Prednisone 1-2 mg/kg/d (oral or IV depending on symptoms/speed of development) If worsening or no improvement, 1-2 mg/kg/d prednisone equivalents and permanently discontinue ICPi treatment Consider RBC transfusion per existing guidelines; do not transfuse more than the minimum number of RBC units necessary to relieve symptoms of anemia or to return a patient to a safe Hgb range (7-8 g/dL in stable, noncardiac inpatients) Should offer patients supplementation with folic acid 1 mg once daily
G4: Life-threatening consequences, urgent intervention indicated	Permanently discontinue ICPi Admit patient Hematology consult IV prednisone corticosteroids 1-2 mg/kg/d

8.0 Hematologic Toxicities	
	
If no improvement or if worsening while on corticosteroids or severe symptoms on presentation, initiate other immunosuppressive drugs, such as rituximab, IVIG, cyclosporin A, and mycophenolate mofetil
 
RBC transfusion per existing guidelines; discuss with blood bank team prior to transfusions that a patient with possible ICPi serious AE is in house.

Additional considerations: Monitor Hgb levels on a weekly basis until the corticosteroid tapering process is complete; thereafter, less-frequent testing is needed	
8.2 Acquired TTP	
Definition: A disorder characterized by the presence of microangiopathic hemolytic anemia, thrombocytopenic purpura, fever, renal abnormalities, and neurologic abnormalities, such as seizures, hemiplegia, and visual disturbances. It is an acute or subacute condition.	

Diagnostic work-up
 
History with specific questions related to drug exposure (e.g, chemotherapy, sirolimus, tacrolimus, opa ER antibiotics, quinine) Physical examination, peripheral smear
 
ADAMTS13 activity level and inhibitor titer
 
LDH, haptoglobin, reticulocyte count, bilirubin, urinalysis to rule out other causes
 
PT, activated PTT, fibrinogen
 
Blood group and antibody screen, direct antiglobulin test, CMV serology
 
Consider CT/MRI brain, echocardiogram, ECG
 
Viral studies
 
Note: This disorder is usually associated with a severe drop in platelets and hemolysis/anemia precipitously
	
Grading	Management
All grades	
The first step in the management of TTP is a high index of suspicion for the diagnosis and timely recognition; hematology consult should immediately be called, as delay in identification is associated with increased mortality/morbidity.
 
Initially, the patient should be stabilized and any critical organ dysfunction stabilized

G1: Evidence of RBC destruction (schistocytosis) without anemia, renal insufficiency, or thrombocytopenia clinically G2: Evidence of RBC destruction (schistocytosis) without clinical consequence with G2 anemia and thrombocytopenia	
Hold ICPi and discuss resumption with patient only after taking into account the risks and benefits, noting that there are currently no data to recommend restarting ICPi therapy Hematology consult
 
Administer 0.5-1 mg/kg/d prednisone

G3: Laboratory findings with clinical consequences (G3 thrombocytopenia, anemia, renal insufficiency > 2) G4: Life-threatening consequences (e.g, CNS hemorrhage or thrombosis/embolism or renal failure)	
For G3: Hold ICPi and discuss resumption with patient only after taking into account the risks and benefits, noting that there are currently no data to recommend restarting ICPi therapy
 
For G4: permanently discontinue ICPi
 
Hematology consult
 
In conjunction with hematology, initiate PEX according to existing guidelines with further PEX dependent on clinical progress
 
Administer methylprednisolone 1 g IV daily for 3 days, with the first dose typically administered immediately after the first PEX
 
May offer rituximab
 
In case of management with rituximab, ICPi treatment will be discontinued

8.0 Hematologic Toxicities	
8.3 Hemolytic uremic syndrome	

Definition: A disorder characterized by a form of thrombotic microangiopathy with renal failure, hemolytic anemia, and severe thrombocytopenia. Signs and symptoms of hemolytic uremic syndrome can include:
 
Bloody diarrhea Decreased urination or blood in the urine Abdominal pain, vomiting, and occasionally fever Pallor Small, unexplained bruises or bleeding from the nose and mouth Fatigue and irritability Confusion or seizures High blood pressure Swelling of the face, hands, feet, or entire body
	

Diagnostic work-up
 
History and physical examination (special consideration for new history of high-risk drugs, hypertension, or cardiac causes) CBC with indices
 
Blood smear morphology. Note that the presence of schistocytes on smear is critical for diagnosis.
 
Serum creatinine ADAMTS13 (to rule out TTP) Homocysteine/methylmalonic acid Complement testing C3, C4, CH50 (complement inhibitory antibodies for suspected familial)
 
Evaluate reticulocyte count and mean corpuscular volume Evaluation of infectious cause, including screening for EBV, CMV, HHV6 Evaluation for nutritional causes of macrocytosis (B12 and folate) Pancreatic enzymes Evaluation for diarrheal causes, shiga toxin, Escherichia coli 0157, etc Direct antibody test (Coombs test), haptoglobin, LDH, and other etiologies of anemia Evaluation for common drugs causing hemolysis (tacrolimus, cyclosporine, sirolimus, etc) Evaluation for concurrent confusion
	
Grading	Management
G1-2: Evidence of RBC destruction (schistocytosis) without clinical consequences of anemia, thrombocytopenia Grade 2	For G1 and G2: Continue ICPi with close clinical follow-up and laboratory evaluation Supportive care
G3: Laboratory findings with clinical consequences (e.g. renal insufficiency, petechiae) G4: Life-threatening consequences (e.g. CNS thrombosis/ embolism or renal failure)	For G3 and G4: Permanently discontinue ICPi Begin therapy with eculizumab therapy 900 mg weekly for four doses, 1,200 mg week 5, then 1,200 mg every 2 weeks Red blood transfusion according to existing guidelines
8.4 Aplastic anemia	

Definition: Condition in which the body stops producing enough new blood cells
 
Diagnostic work-up
 
History and physical examination (close attention to medications, exposure to radiation, toxins, recent viral infections) CBC, smear, reticulocyte count
 
Viral studies, including CMV, HHV6, EBV, parvovirus
 
Nutritional assessments including B12, folate, iron, copper, ceruloplasmin, vitamin D
 
Serum LDH, renal function
 
Work-up for infectious causes
 
Identify marrow hypo/aplasia
 
Bone marrow biopsy and aspirate analysis
 
Peripheral blood analysis, including neutrophil count, proportion of GPI-negative cells by flow for PNH
 
Flow cytometry to evaluate loss of GPI-anchored proteins
	

8.0 Hematologic Toxicities	
Type and screen patient for transfusions and notify blood bank that all transfusions need to be irradiated and filtered	
Grading	Management
G1: Nonsevere, < 0.5 polymorphonuclear cells $\times 10^9/L$ hypocellular marrow, with marrow cellularity < 25%, peripheral platelet count > 20,000, reticulocyte count < 20,000	Hold ICPi and provide growth factor support and close clinical follow-up, and laboratory evaluation Supportive transfusions as per local guidelines
G2: Severe, hypocellular marrow < 25% and two of the following: ANC < 500, peripheral platelet < 20,000, and reticulocyte < 20,000	Hold ICPi and provide growth factor support and close clinical laboratory evaluations daily Administer ATG + cyclosporine; HLA typing and evaluation for bone marrow transplantation if patient is candidate; all blood products should be irradiated and filtered Supportive care with granulocyte colony-stimulating factor may be added in addition
G3-4: Very severe, ANC > 200, platelet count > 20,000, reticulocyte count > 20,000, plus hypocellular marrow > 25%	For G3: Hold ICPi and monitor weekly for improvement; if not resolved, discontinue treatment until AE has reverted to G1 For G4: permanently discontinue ICPi Hematology consult, growth factor support Horse ATG plus cyclosporine If no response, repeat immunosuppression with rabbit ATG plus cyclosporine, cyclophosphamide For refractory patients, consider eltrombopag plus supportive care

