8.6 Immune thrombocytopenia	
Definition: An autoimmune disorder characterized by immunologic destruction of otherwise normal platelets	
Diagnostic work-up	
History and physical examination (special attention for lymphocyte-depleting therapy, such as fludarabine, ATG, corticosteroids, cytotoxic therapy) Family history of autoimmunity or personal history of autoimmune disease
 
History of viral illness
 
CBC
 
Peripheral blood smear, reticulocyte count
 
Bone marrow evaluation only if abnormalities in the above test results and further investigation is necessary for a diagnosis
 
Patients with newly diagnosed immune thrombocytopenia should undergo testing for HIV, hepatitis C virus, hepatitis B virus, and Helicobacter pylori Direct antigen test should be checked to rule out concurrent Evan syndrome
 
Nutritional evaluation
 
Bone marrow evaluation if other cell lines affected and concern for aplastic anemia

Grading	Management
G1: Platelet count < 100/ μ L G2: Platelet count < 75/ μ L	
Continue ICPi with close clinical follow-up and laboratory evaluation
 
Hold ICPi but monitor for improvement; if not resolved, interrupt treatment until AE has reverted to G1
 
Administer prednisone 1 mg/kg/d (dosage range, 0.5-2 mg/kg/d) orally for 2-4 weeks after which time this medication should be tapered over 4-6 weeks to the lowest effective dose IVIG may be used in conjunction with corticosteroids if a more-rapid increase in platelet count is required.

G3: Platelet count < 50/ μ L	
Hold ICPi but monitor for improvement; if not resolved, interrupt treatment until AE has reverted to G1

G4: Platelet count < 25/ μ L	
Permanently discontinue ICPi
 
Hematology consult
 
Prednisone 1-2 mg/kg/d (oral or IV depending on symptoms)
 
If worsening or no improvement, 1-2 mg/kg/d prednisone equivalents and permanently discontinue treatment
 
IVIG used with corticosteroids when a more-rapid increase in platelet count is required
 
If IVIG is used, the dose should initially be 1 g/kg as a one-time dose. This dosage may be repeated if necessary

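### Two grading rows in Protocol Appendix 5, Table A8 are wrong on the protocol's own text: aplastic anemia Grade 3-4 runs opposite to Grade 2, and the immune thrombocytopenia platelet limits are printed about 1,000-fold too low

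*Protocol*

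**What the plan says.** Table A8 in Protocol Appendix 5 gives sites a grade description and an action for each immune-related blood disorder.

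**8.4, aplastic anemia.** The condition is defined as too little production of new blood cells, so lower counts are worse.
- Grade 2: "G2: Severe, hypocellular marrow < 25% and two of the following: ANC < 500, peripheral platelet < 20,000, and reticulocyte < 20,000".
- Grade 3-4: "G3-4: Very severe, ANC > 200, platelet count > 20,000, reticulocyte count > 20,000, plus hypocellular marrow > 25" (the last figure is a percentage).
- Drug is held at Grades 1, 2 and 3. For Grade 4 the table says "For G4: permanently discontinue ICPi Hematology consult, growth factor support".

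**8.6, immune thrombocytopenia.** The four grades are platelet limits, all printed per microliter. They run from "G1: Platelet count < 100" through 75 and 50 to "G4: Platelet count < 25". Drug continues at Grade 1. At Grades 2 and 3 the action is "Hold ICPi but monitor for improvement; if not resolved, interrupt treatment until AE has reverted to G1". At Grade 4 it is stopped for good.

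**Related text.** Inclusion criterion 8a in Section 5.1 requires platelets of at least 100 x 10^9/L. Section 6.9.2 and the introduction to Appendix 5 both name these two conditions among those where Grade 4 requires a permanent stop.

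**The concern.** Within 8.4, the category called very severe is described by higher counts and a fuller marrow than the category called severe. Read literally, it excludes the patients with the emptiest marrow and can admit patients with much better counts.

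Within 8.6, a patient would need fewer than 100 platelets per microliter to reach even Grade 1. Yet the protocol's entry floor has the same digits in units of 10^9/L, and 8.4 in the same table treats a platelet count below 20,000 as a criterion for severe disease.

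These are decision thresholds in the appendix to which Section 6.8 sends sites for Grade 3 and Grade 4 immune-related events, and both toxicities carry a mandatory Grade 4 stop. At stake is whether a site that applies the printed cells literally would place a patient in the right category. No estimate, test or sample size depends on them.

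**Working it through.** The plan states no derived figure to reproduce, so the check is one of logic and units.

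**1. Units in 8.4.** The Grade 2 and Grade 3-4 counts carry no unit. Grade 1 is "G1: Nonsevere, < 0.5 polymorphonuclear cells" x 10^9/L. Since 1 x 10^9/L = 1,000 per microliter, 0.5 x 10^9/L = 500 per microliter. That equals the Grade 2 ANC limit of 500, so the counts in 8.4 are per microliter.

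**2. Direction in 8.4.**

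| Quantity | Grade 2 | Grade 3-4 as printed |
|---|---|---|
| Marrow | < 25% | > 25% |
| ANC | < 500 | > 200 |
| Platelets | < 20,000 | > 20,000 |
| Reticulocytes | < 20,000 | > 20,000 |

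The marrow limit and two of the three counts are needed for Grade 2; all four limits are listed for Grade 3-4.

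**3. Can one patient meet both?** Grade 2 requires marrow < 25%, which fails the Grade 3-4 marrow limit. Any two of the three Grade 2 counts include platelets or reticulocytes, and a value below 20,000 fails the matching Grade 3-4 limit. Every Grade 2 patient therefore fails at least 2 of the 4 limits, and the overlap is empty.

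Two illustrative patients:
- ANC 100, platelets 10,000, reticulocytes 10,000, marrow 10%: meets Grade 2 and fails all four printed Grade 3-4 limits.
- ANC 1,500 and platelets 100,000 (the entry floors of 1.5 and 100 x 10^9/L), with assumed reticulocytes of 50,000 and marrow of 30%: fails Grade 2 and meets all four printed Grade 3-4 limits.

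**4. With the signs reversed.** Grade 3-4 becomes ANC < 200, platelets < 20,000, reticulocytes < 20,000 and marrow < 25%. Since 200 < 500 and the other limits match, every such patient also satisfies Grade 2. The worse category then sits inside the milder one, and the first patient above moves to Grade 3-4.

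**5. Platelet limits in 8.6.** The entry floor is 100 x 10^9/L = 100,000 per microliter.

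| Grade | Printed, per microliter | Printed, in 10^9/L | Same digits read as 10^9/L, per microliter |
|---|---|---|---|
| 1 | 100 | 0.100 | 100,000 |
| 2 | 75 | 0.075 | 75,000 |
| 3 | 50 | 0.050 | 50,000 |
| 4 | 25 | 0.025 | 25,000 |

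Grade 1 against the entry floor: 100,000 / 100 = 1,000 exactly. For Grades 2 to 4 there is no separate yardstick, so the factor of 1,000 is inferred from the shared unit and the sequence of digits. The limit of 20,000 in 8.4 supports it: 20,000 / 100 = 200 times the printed Grade 1 limit, and 20,000 / 25 = 800 times the printed Grade 4 limit.

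**6. Size of the gap in 8.6, if 10^9/L is meant.** The printed row gives no grade from 100 up to 100,000 per microliter. It omits the Grade 2 hold from 75 up to 75,000 and the Grade 4 stop from 25 up to 25,000. A count of 20,000 per microliter has no printed grade; on the corrected scale 20,000 < 25,000, so it is Grade 4.

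**The case against.** The strongest reply is that these cells do not assign the grade. Section 6.8 bases toxicity grading on NCI-CTCAE v5.0, Section 6.9.2 ties treatment of immune-related events mainly to severity on that scale, and Appendix 4 has investigators refer to it. The Grade 4 stops for both conditions stand in Section 6.9.2, whatever Table A8 prints. Key blood counts are reviewed within 3 days before dosing (Appendix 6). Appendix 5 is framed as recommendations drawn from published guidelines, and neither condition is among the immune-related risks listed in Section 6.9.2. SAP 15.3 grades laboratory values by NCI-CTCAE v5.0, and SAP 15.2.3.2 identifies immune-related events from preferred terms, timing and case report form answers. All of this stands. It limits the consequence without making the two rows correct.

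A reader might infer from 8.4 that the printed route to the Grade 4 permanent stop has been lost. The documents do not support that. The row gives one description for Grades 3 and 4 together but different actions for each, so it cannot separate the Grade 3 hold from the Grade 4 stop, before or after correction. Drug is held at Grades 1 to 3 in any case. What the printed row fails to do is identify the worse category.

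A reader might also infer from 8.6 that a patient with 20,000 platelets per microliter would go ungraded and stay on drug. That is true only of this row read in isolation, because NCI-CTCAE v5.0 still applies.

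A text-reading fault is a fair question. It is unlikely for 8.4, where four signs in one cell would have to flip while the Grade 2 cell beside it kept its own. In 8.6 the same unit appears at all four grades. A check of the signed PDF settles both.

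**Conclusion.** Both rows are wrong on the protocol's own text. In 8.4, all four Grade 3-4 limits point the opposite way to Grade 2, and no patient can meet both. In 8.6, the Grade 1 limit is exactly 1,000-fold below the entry floor, and Grades 2 to 4 are very probably low by the same factor.

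This rests on two assumptions: that the signed document prints what the extracted text shows, and that the 8.6 digits were meant in 10^9/L. Whether the rows copy a source guideline as it stands cannot be checked from these documents.

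The point is a minor safety-text correction. No endpoint or analysis changes. SAP 4.1 records early discontinuation and a low number of participants, which lowers the urgency; the documents do not say whether anyone remains on drug.

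**What to change.** Check both rows against the signed PDF. If they stand, then with medical confirmation:

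- 8.4, Grade 3-4: change to ANC < 200, platelets < 20,000, reticulocytes < 20,000 and marrow < 25%.
- 8.6: change the Grade 1 to 4 limits to 100, 75, 50 and 25 x 10^9/L.
- Notify any site with a participant still on drug.

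The 8.4 change restores the order of severity. Separating Grade 3 from Grade 4 would still rest on NCI-CTCAE v5.0.

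The cost is a short protocol clarification or amendment to two located rows, plus a site notice where one is needed. Sample size, data collection and analysis are unaffected.
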